4.1.2 Cohort 2 Design

Subjects in cohort 2 will receive both AMG 330 and pembrolizumab on day 1. All cycles are 57 days in duration. Pembrolizumab will be administered at a dose of 200 mg (Q3W) by a 30-minute IV infusion. The subject will then receive dexamethasone 8 mg. Dexamethasone will be given 1 hour prior to each step dose of AMG 330. If the subject does not develop a \geq grade 2 infusion reaction, or if the infusion reaction is reversible after the 1-hour observation period, the subject will start AMG 330 at a starting dose of [REDACTED] μ g/day for 3 days, followed by [REDACTED] μ g/day for 4 days, followed by [REDACTED] μ g/day for 7 days, and continue dosing as per [Table 4-3](#), increasing dose levels every 7 days up to [REDACTED] μ g/day as tolerated by subjects. Pembrolizumab will be administered at 200 mg IV once every 3 weeks. Subjects will continue [REDACTED] μ g/day of AMG 330 and pembrolizumab for 14 days. Cycle 1 will be followed by a 1-week interval without AMG 330 administration, and administration of pembrolizumab will continue non-interrupted on Q3W schedule. The AMG 330-infusion free interval may be extended up to 4 weeks (depending on safety, treatment response, and in case of prolonged marrow aplasia and cytopenia in aleukemic subjects) after consultation with the sponsor. Cycle 2 and all subsequent cycles will start with the initiation of AMG 330 administration and include the same step dose levels and duration as in cycle 1. The duration of AMG 330 step dose levels in cycle 2 and beyond can be shortened to 2 to 5 days if a subject tolerated the

investigational product in cycle 1 and based on the discussion and agreement between the investigator and the sponsor.

Table 4-3. Dosing for Cohort 2 (All Cycles)

AMG 330 Dose Level (μ g/day, cIV)	AMG 330 Days Administered	Pembrolizumab Days Administered (IV infusion)
	D1-3	D1
	D4-7	
	D8-14	
	D15-21	
	D22-28	D22
	D29-35	
	D36-42	
	D43-56	D43
(infusion-free period)	D57-64	

cIV = continuous intravenous; D = day; IV = intravenous

The overall study design is described by a study schema in [Section 1.2](#). The endpoints are defined in [Section 3](#).

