Cycle 2 will start with the initiation of AMG 330 administration and include the same step dose levels and duration as in cycle 1 with the exception of the █ and █ µg/day dose levels, which will be shortened from 14 days to 7 days (Table 4-2). The duration of AMG 330 step dose levels in cycle 2 and beyond can be shortened to 2 to 5 days if a subject tolerated the investigational product in cycle 1 and based on the discussion and agreement between the investigator and the sponsor. All subsequent cycles will be conducted similarly to cycle 2.

On days when pembrolizumab administration and an AMG 330 dose level increase will occur, the subject will receive dexamethasone 8 mg at the conclusion of the pembrolizumab infusion. Dexamethasone will be given 1 hour prior to increasing the AMG 330 dose. If the subject does not develop a ≥ grade 2 infusion reaction, or if the

infusion reaction is reversible after the 1-hour observation period, AMG 330 may be increased to the next dose level, as shown in [Table 4-2](#).

Table 4-2. Dosing for Cohort 1 (Cycle 2 and Beyond)

AMG 330 Dose Level (μ g/day, clV)	AMG 330 Days Administered	Pembrolizumab Days Administered (IV infusion)
	D1-3	
	D4-7	
	D8-14	
	D15-21	D15
	D22-28	
	D29-35	
	D36-42	D36
	D43-56	
(infusion period)	D57-64	D57

clV = continuous intravenous; D = day; IV = intravenous

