6.2 Dose Modification

6.2.1 Dose-cohort Study Escalation/De-escalation and Stopping Rules, Dose-Limiting Toxicities (DLTs)

Step Dose Level Determination

A decision to proceed with the next step dose of AMG 330 for each subject in cohorts 1 and 2 will be based on investigator's assessment of safety and upon approval by Sponsor.

In cohort 1, a sentinel subject will be treated first. The minimal interval between treatment start for the sentinel subject and other subjects in the cohort is 21 days. If the sentinel subject has not experienced a DLT by day 14 at █ µg/day AMG 330, he/she will proceed with 200 mg pembrolizumab on day 15 and remain at an AMG 330 dose level of █ µg/day for 7 days (until day 21). If the sentinel subject experiences a DLT during the first 7 days of treatment with AMG 330 at █ µg/day, this subject will be replaced, but the DLT will still be counted towards the study stopping rules. If the sentinel subject does not experience a DLT before or on day 21, the next subjects in the cohort may initiate dosing. If a sentinel subject experiences a DLT, the sponsor will issue a decision based on the evaluation of clinical significance of the adverse event by the DLRT and potential decisions by the sponsor may include stopping AMG 330 and/or pembrolizumab, dose de-escalation of AMG 330, or continuing therapy at full dose.

Cohort 2 will be initiated only after all subjects in cohort 1 completed study day 28 (ie, AMG 330 █ µg/day dose level in combination with pembrolizumab for 7 days), and if the rate of DLT is ≤ 3 out of 10 subjects. After receiving the DLRT recommendation, sponsor will render a final decision and will issue a written notification of the decision to investigators. Further information on dose level review meetings (DLRMs) is provided in [Section 11.3](#).

Individual Stopping Rules

Dosing for an individual will be stopped for any occurrence of a DLT. The event will be reviewed by the investigator and Sponsor for evidence of relationship to treatment and

clinical or medical significance to decide whether dosing may be resumed for the individual and any modifications to the dosing, if appropriate.

Dose Limiting Toxicities

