A DLT will be defined as any of the events described below occurring in a subject during the DLT window, unless clearly attributable to causes other than investigational product. The DLT window will start on day 1 and last for the duration of cycle 1. The CTCAE v5 will be used to assess toxicities/adverse events with the exception of CRS (see [Table 6-5](#) for grading of CRS).

DLT Evaluation

To be DLT evaluable, subjects must meet 1 of the following criteria during DLT evaluation period (cycle 1 day 1 to cycle 1 end of infusion):

- The subject experienced a DLT; OR
- The subject has received at least 70% of planned cumulative dose of AMG 330 and has not missed more than 1 dose of pembrolizumab; OR
- The subject did not experience a DLT and completed the DLT evaluation period

Events listed below are to be considered as DLTs and exceptions when occurring in a subject during the DLT window unless clearly attributable to causes other than AMG 330 and pembrolizumab treatment:

- Any treatment-related death.
- Grade 4 neutropenia lasting \geq 4 weeks from last day of cycle in absence of evidence of active AML. Note: grade 4 neutropenia maybe assessed retrospectively and outside of the DLT window
- Grade 3–4 non-hematologic toxicity not clearly resulting from the underlying leukemia EXCEPT:
 - Grade 3 fatigue, asthenia, fever, anorexia, or constipation
 - Grade 3 nausea, vomiting or diarrhea not requiring tube feeding, total parenteral nutrition, or requiring or prolonging hospitalization
 - Infection, bleeding, or other expected direct complication of cytopenias due to active underlying leukemia
 - Grade 3 infusion reaction, unless attributed to pembrolizumab, if successfully managed and which resolves within 72 hours
 - Grade 3 rash or pruritus
 - Grade 3 or 4 tumor lysis syndrome if it is successfully managed clinically and resolves within 7 days without end-organ damage.

Approved

- Grade 3 or 4 isolated analyte abnormalities (ie, those occurring without clinical consequence) that resolve, with or without intervention, to < grade 2 levels in < 72 hours will not be considered DLT.
- Grade 3 or 4 asymptomatic enzyme elevations including aspartate aminotransferase (AST), alanine aminotransferase (ALT) (without bilirubin elevation), gamma glutamyl transferase that resolve, with or without intervention, to ≤ grade 2 within 7 days will not be considered a DLT, unless attributed to pembrolizumab.

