Grade 2 Requires therapy or infusion interruption but responds promptly to symptomatic treatment (eg, antihistamines, NSAIDs, narcotics, IV fluids); prophylactic medications indicated for ≤ 24 hrs.	
 Stop Infusion. Additional appropriate medical therapy may include but is not limited to: 
 IV fluids Antihistamines NSAIDs Acetaminophen Narcotics Increase monitoring of vital signs as medically indicated until the participant is deemed medically stable in the opinion of the investigator. If symptoms resolve within 1 hour of stopping drug infusion, the infusion may be restarted at 50% of the original infusion rate (eg, from 100 mL/hr to 50 mL/hr). Otherwise dosing will be held until symptoms resolve and the participant should be premedicated for the next scheduled dose. 
Participants who develop grade 2 toxicity despite adequate premedication should be permanently discontinued from further study drug treatment
	Participant may be premedicated 1.5h (± 30 minutes) prior to infusion of pembrolizumab with: Diphenhydramine 50 mg po (or equivalent dose of antihistamine). Acetaminophen 500-1000 mg po (or equivalent dose of analgesic).
Grades 3 or 4 Grade 3: Prolonged (ie, not rapidly responsive to symptomatic medication and/or brief interruption of infusion); recurrence of symptoms following initial improvement; hospitalization indicated for other clinical sequelae (eg, renal impairment, pulmonary infiltrates) Grade 4: Life-threatening; pressor or ventilator support indicated	
 Stop Infusion. Additional appropriate medical therapy may include but is not limited to: 
 Epinephrine** IV fluids Antihistamines NSAIDs Acetaminophen Narcotics Oxygen Pressors Corticosteroids Increase monitoring of vital signs as medically indicated until the participant is deemed medically stable in the opinion of the investigator. Hospitalization may be indicated. 
**In cases of anaphylaxis, epinephrine should be used immediately.
 
Participant is permanently discontinued from further study drug treatment.
	No subsequent dosing
Appropriate resuscitation equipment should be available at the bedside and a physician readily available during the period of drug administration. For further information, please refer to the CTCAE v5.0 at http://ctep.cancer.gov		

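### On cohort 2 day 1, a grade 3 or 4 pembrolizumab infusion reaction judged reversible at one hour triggers both an instruction to start AMG 330 and an instruction to stop dosing

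*Protocol*

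**What the plan says.** Protocol Section 4.1.2 sets the order of treatment: "Subjects in cohort 2 will receive both AMG 330 and pembrolizumab on day 1". Pembrolizumab comes first, then dexamethasone, then AMG 330 after an observation hour. AMG 330 follows if there was no infusion reaction of grade 2 or higher, "or if the infusion reaction is reversible after the 1-hour observation period, the subject will start AMG 330 at a starting dose". The synopsis (Cohort 2 Design) and SAP Section 3.1.2 repeat this rule.

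Protocol Section 6.2.1 defines the DLT. On timing it says "The DLT window will start on day 1 and last for the duration of cycle 1". It counts grade 3 or 4 "non-hematologic toxicity not clearly resulting from the underlying leukemia EXCEPT" a list of exceptions. One exception is "Grade 3 infusion reaction, unless attributed to pembrolizumab, if successfully managed and which resolves within 72 hours". On the individual subject it says "Dosing for an individual will be stopped for any occurrence of a DLT"; the investigator and sponsor then review the event and decide whether dosing may resume.

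Protocol Section 6.2.2.1 contains three further rules:
- After a grade 4 non-hematologic event the subject gets no more protocol therapy unless the sponsor and investigators agree otherwise.
- A DLT calls for immediate infusion interruption.
- A DLT is listed as a reason for permanent discontinuation of investigational product, with an exception for clear clinical benefit.

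Table 6-4, on pembrolizumab infusion reactions, says for grades 3 and 4: "Participant is permanently discontinued from further study drug treatment".

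**The concern.** The start rule in Section 4.1.2 has a lower grade bound and no upper one. Read literally, it covers a grade 3 or 4 reaction as long as that reaction is reversible at the end of the hour. Those are the reactions that Section 6.2.1 makes DLTs and answers with a stop. A site working from the dosing section would give the first AMG 330 dose soon after a protocol-defined DLT. A site working from the DLT section would hold it and call for review. No section says which rule prevails.

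At stake is whether a subject who has just had a severe reaction receives a second agent the same day, and whether sites handle that situation alike. A secondary loss is interpretability: among subjects with a day 1 DLT, AMG 330 exposure would depend on which section the site consulted.

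**Working it through.** The point involves no stated figure. The check is to apply each rule to one subject: cohort 2, day 1, with an infusion reaction that is reversible after the observation hour.

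1. **Attribution.** AMG 330 has not started. Pembrolizumab has been infused and dexamethasone given after it. Pembrolizumab is the natural attribution, although the investigator still makes it.
2. **DLT status at grade 3.** The exception for a managed grade 3 reaction that resolves within 72 hours is withdrawn when the reaction is attributed to pembrolizumab. Reversal therefore does not remove DLT status.
3. **DLT status at grade 4.** The infusion-reaction exception covers grade 3 only, so grade 4 is a DLT.
4. **Window.** It opens on day 1, so the first pembrolizumab infusion lies inside it.
5. **Clinical-benefit exception (Section 6.2.2.1).** Benefit cannot have been shown before the first AMG 330 dose, so this exception gives no route to a same-day start.

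Side by side:

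| Reversible reaction on day 1 | Section 4.1.2 | Section 6.2.1 | Section 6.2.2.1 |
|---|---|---|---|
| Grade 2 | Start AMG 330 | Not a DLT under the grade 3-4 criterion | No mandatory stop |
| Grade 3, attributed to pembrolizumab | Start AMG 330 | DLT; dosing stopped pending review | Permanent discontinuation unless clear benefit |
| Grade 4 | Start AMG 330 | DLT; dosing stopped pending review | As for grade 3; also no further therapy unless sponsor and investigators agree |

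The grade 2 row is consistent. The other two rows conflict without any appeal to Table 6-4.

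**Effect on the primary endpoint.** Section 6.2.1 makes any subject with a DLT evaluable, and Section 9.4.2.3.1 tabulates subject incidence. With n evaluable subjects in cohort 2, this subject contributes 1/n if AMG 330 is withheld and 1/n if it is started, so the difference is 1/n - 1/n = 0. A second DLT after AMG 330 would not change the subject count. The Safety Analysis Set (Protocol Section 9.3.1, SAP Section 6.1) needs one dose of either product, so membership is the same. The cohort 2 sentinel test in Section 4.1 asks whether a DLT occurred in the first 7 days, and the answer is yes under both rules.

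**Neighbouring text.** Section 4.1.1 (cohort 1, cycle 2 and beyond; repeated in SAP Section 3.1.1) also sets no upper grade: if the "infusion reaction is reversible after the 1-hour observation period, AMG 330 may be" stepped up. Those cycles lie outside the DLT window. The wording conflicts with the grade 4 rule in Section 6.2.2.1, and with Table 6-4 only if that table's term study drug includes AMG 330.

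**The case against.** The strongest reply is that the overlap is almost empty. Table 6-4 describes grade 3 as prolonged and not rapidly responsive, as recurring after improvement, or as needing hospitalization for sequelae. Grade 4 is life-threatening. The one-hour test also resembles the grade 2 row, where resolution within an hour permits a restart of the infusion. On this reading the drafters meant reversibility to separate grade 2 from worse. This stands as to frequency: the case is uncommon. It does not remove the conflict. Reversible is not defined and need not mean resolved, and the recurrence, hospitalization and pressor-support criteria do not turn on duration.

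A second reply is that Section 6.2.1 allows dosing to resume and requires sponsor approval of step doses. Resumption comes only after review, whereas Section 4.1.2 directs a same-day start without one. The approval is written for the next step dose, not for the first start.

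Third, Table 6-4 may mean pembrolizumab alone. It sits in the pembrolizumab section, and Section 4.1 allows AMG 330 to continue alone after pembrolizumab stops. Against that, inclusion criterion 107 uses study drug for either product. The scope is unclear, so Table 6-4 is secondary support only.

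A reader might also infer that the conflict shifts the cohort 2 DLT rate, for example by 1/10 = 10 percentage points, or 1/6 = about 17 at the minimum of 6 evaluable subjects. Those figures are the weight of any single DLT. The inconsistency itself contributes nothing, because the event is a DLT either way. Nor does the start rule extend to cohort 2 days 22 and 43: same-day step increases fall under Section 6.1.1.4, which asks that the pembrolizumab dose be well tolerated. AMG 330 is also already running on those days, so attribution to pembrolizumab no longer follows from the order of dosing.

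**Conclusion.** The contradiction is real and confined to a narrow case: a cohort 2 subject on day 1 with a grade 4 reaction, or a grade 3 reaction attributed to pembrolizumab, that is judged reversible after one hour. For that subject Section 4.1.2 directs a start of AMG 330, while Sections 6.2.1 and 6.2.2.1 direct a stop, pending review or permanently. The documents give no frequency for such reactions, so the expected number of subjects cannot be stated.

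The consequence is for AMG 330 exposure and subject safety. The DLT numerator and denominator, the analysis sets and the sentinel decision are unaffected. The conclusion assumes that the day 1 reaction is attributed to pembrolizumab (for grade 3) and that reversible can apply to a grade 3 or 4 reaction. It does not depend on how Table 6-4 is read. The uncapped wording for cohort 1, cycle 2 and beyond, is a lesser point: it conflicts with the grade 4 rule, and with Table 6-4 only on the broad reading.

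**What to change.** Reconcile the synopsis, Protocol Sections 4.1.1, 4.1.2 and 6.1.1.4 and SAP Sections 3.1.1 and 3.1.2 with Protocol Sections 6.2.1 and 6.2.2.1 and Table 6-4. State in one place, by grade and separately for AMG 330 and pembrolizumab, what follows a pembrolizumab infusion reaction. Say which products study drug covers in Table 6-4, and define reversible if the term is kept. Cross-refer to that place from Sections 4.1.1 and 4.1.2. Which rule stands is for the sponsor to decide.

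The cost is a wording amendment to the protocol and the mirrored SAP text, with no added subjects, procedures or analyses. It is best done before cohort 2 opens.

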4.2 Number of Subjects

It is anticipated that approximately 20 subjects will be enrolled in the study, with at least 6 DLT evaluable subjects in each cohort. With 6 evaluable subjects in 1 cohort, there is an 82% chance of observing at least 1 DLT if the true DLT rate is 25%. For cohort 1, at least 10 subjects will be dosed through study day 28.

Participants in this clinical investigation shall be referred to as “subjects”. For the sample size justification, see [Section 9.2](#).

4.2.1 Replacement of Subjects

Ineligible subjects (ie, subjects who were exposed to AMG 330 or pembrolizumab, but post hoc were found to be ineligible) may be replaced. Subjects who do not meet the DLT evaluable criteria (see [Section 6.2.1](#)) may be replaced until at least 6 subjects become DLT evaluable in each cohort or at least 10 subjects in cohort 1 have been dosed through study day 28. If a sentinel subject in cohort 1 experiences a DLT at [REDACTED] μ g/day, [REDACTED] μ g/day or [REDACTED] μ g/day of AMG 330 during the first 14 days of monotherapy treatment in cycle 1, this subject will be defined as DLT evaluable and will not proceed

with the combination regimen. The sentinel role will be re-assigned to the next available subject.

4.2.2 Number of Sites

Approximately 5 investigative sites in the United States will be included in the study.

Sites that do not enroll subjects within 6 months of site initiation may be closed.

4.3 Justification for Investigational Product Dose

Justification for AMG 330 Dose

The planned dosing schedule for AMG 330 will evaluate doses that have been tested in the ongoing first-in-human study (Amgen Study 20120252) in subjects with R/R AML.

Planned dose levels for step dose escalation will be as follows: [REDACTED]

[REDACTED] and [REDACTED] µg/day. The rationale for selecting these dose levels for the combination study includes following findings generated during the phase 1 dose escalation study: each of the proposed doses has been tested as a monotherapy and deemed safe and tolerable, and proposed dose levels include efficacious doses (CR/CRI have been reported at [REDACTED] and [REDACTED] µg dose levels).

As of 17 June 2019, treatment-emergent adverse events (TEAEs) were reported for 47 (95.9%) of 49 subjects. Forty subjects (81.6%) had grade ≥ 3 adverse events, 33 subjects (67.3%) had serious adverse events, and 2 subjects (4.1%) had fatal adverse events. Six subjects (12.2%) had adverse events that led to discontinuation of AMG 330. Dose-limiting toxicities (DLTs) were reported for 6 subjects. The most frequently reported adverse event by preferred term was CRS (31 subjects, 63.3%). Adverse events considered by the investigator to be related to AMG 330 were reported for 43 subjects (87.8%), the most frequently reported treatment-related adverse events (subject incidence $\geq 20\%$) were CRS (63.3%), rash (30.6%), febrile neutropenia (22.4%), and nausea (20.4%).

CRS mitigation approach developed for AMG 330 and implemented into the ongoing first in human study allows resolution of CRS within 7 days. Thus, the duration of each step dose is defined as at least 7 days to allow monitoring the frequency, severity and resolution dynamics of CRS in subjects treated with the combination regimen. An exception is given for first 2 lower doses ([REDACTED] µg/day and [REDACTED] µg/day), duration for which will be 3 and 4 days respectively, since the occurrence of CRS is rare at these doses due to the current CRS mitigation approach (ie, premedication with dexamethasone 8 mg 1 hour prior to each step dose of AMG 330).

As of the 17 June 2019 data snapshot date, 5 of 39 evaluable subjects had a response. One subject (cohort 11 [REDACTED] µg/day) achieved CR, 3 subjects (1 each in cohort 8 [REDACTED] µg/day], cohort 9 [REDACTED] µg/day], and cohort 12 [REDACTED] µg/day]) achieved CRI, and 1 subject (cohort 2 [REDACTED] µg/day]) achieved morphologic leukemia-free state (MLFS). The objective response rate based on subjects who achieved either a CR, CRI, CR with partial hematologic recovery (CRh), partial remission (PR), or MLFS was 12.8% (80% CI: 6.4%, 22.5%). Two additional subjects in cohort 15 ([REDACTED] µg/day) achieved CR (1 subject) and CRI (1 subject) after the data snapshot date of 17 June 2019.

Refer to the [AMG 330 Investigational Brochure](#) for further information.

Justification for Pembrolizumab Dose

The planned dose of pembrolizumab for this study is 200 mg every 3 weeks (Q3W). Based on the totality of data generated in the Keytruda development program, 200 mg Q3W is the appropriate dose of pembrolizumab for adults across all indications and regardless of tumor type. As outlined below, this dose is justified by:

- Clinical data from 8 randomized studies demonstrating flat dose and exposure-efficacy relationships from 2 mg/kg Q3W to 10 mg/kg every 2 weeks (Q2W),
- Clinical data showing meaningful improvement in benefit-risk including overall survival at 200 mg Q3W across multiple indications, and
- Pharmacology data showing full target saturation in both systemic circulation (inferred from pharmacokinetic [PK] data) and tumor (inferred from physiologically-based PK analysis) at 200 mg Q3W.

Among the 8 randomized dose-comparison studies, a total of 2262 participants were enrolled with melanoma and non-small cell lung cancer, covering different disease settings (treatment naïve, previously treated, PD-L1 enriched, and all-comers) and different treatment settings (monotherapy and in combination with chemotherapy). Five studies compared 2 mg/kg Q3W versus 10 mg/kg Q2W (KN001 Cohort B2, KN001 Cohort D, KN002, KN010, and KN021), and 3 studies compared 10 mg/kg Q3W versus 10 mg/kg Q2W (KN001 Cohort B3, KN001 Cohort F2, and KN006). All of these studies demonstrated flat dose and exposure-response relationships across the doses studied representing an approximate 5- to 7.5-fold difference in exposure. The 2 mg/kg (or 200 mg fixed-dose) Q3W provided similar responses to the highest doses studied. Subsequently, flat dose and exposure-response relationships were also observed in other tumor types including head and neck cancer, bladder cancer, gastric cancer and

Approved

classical Hodgkin Lymphoma, confirming 200 mg Q3W as the appropriate dose independent of the tumor type. These findings are consistent with the mechanism of action of pembrolizumab, which acts by interaction with immune cells, and not via direct binding to cancer cells.

Additionally, pharmacology data clearly show target saturation at 200 mg Q3W. First, PK data in KN001 evaluating target-mediated drug disposition conclusively demonstrated saturation of PD-1 in systemic circulation at doses much lower than 200 mg Q3W. Second, a physiologically-based PK analysis was conducted to predict tumor PD-1 saturation over a wide range of tumor penetration and PD-1 expression. This evaluation concluded that pembrolizumab at 200 mg Q3W achieves full PD-1 saturation in both blood and tumor.

Finally, population PK analysis of pembrolizumab, which characterized the influence of body weight and other participant covariates on exposure, has shown that the fixed-dosing provides similar control of PK variability as weight-based dosing, with considerable overlap in the distribution of exposures from the 200 mg Q3W fixed dose and 2 mg/kg Q3W dose. Supported by these PK characteristics and given that fixed-dose has advantages of reduced dosing complexity and reduced potential of dosing errors, the 200 mg Q3W fixed-dose was selected for evaluation across all pembrolizumab protocols.

